Fasting Versus Non-fasting prior to elective Cardiac catheterisation

Chief Investigator: [name]

Principal Investigator: [name]

Research Trust: Blackpool Teaching Hospitals NHS Foundation Trust

Funder: Blackpool Teaching Hospitals NHS Foundation Trust

Sponsor: Blackpool Teaching Hospitals NHS Foundation Trust

Date of Submission: 12/10/2017

Table of Contents

1	STUDY SUMMARY	4
2	INTRODUCTION	6
2.1	BACKGROUND.....	6
2.2	STUDY OBJECTIVES.....	8
3	STUDY DESIGN	9
3.1	GENERAL	9
3.2	STUDY PROCEDURE.....	9
3.3	PRIMARY STUDY ENDPOINTS	10
3.4	SECONDARY STUDY ENDPOINTS	10
3.5	END OF STUDY	10
4	METHODS	10
4.1	SUBJECT SELECTION AND WITHDRAWAL.....	10
4.1.1	Inclusion Criteria	11
4.1.2	Exclusion Criteria	11
4.2	SUBJECT RECRUITMENT AND SCREENING	11
4.3	RANDOMISATION PROCESS	11
4.4	INFORMED CONSENT.....	12
4.5	WITHDRAWAL OF SUBJECTS	12
5	PRIOR AND CONCOMITANT THERAPY	12
6	CLINICAL PROCEDURES	12
7	STATISTICAL PLAN	12
7.1	SAMPLE SIZE DETERMINATION	13
7.2	STATISTICAL METHODS	13
7.3	INTERIM ANALYSES	13
7.4	SUBJECT POPULATION(S) FOR ANALYSIS	13
8	SAFETY AND ADVERSE EVENTS	13
8.1	RECORDING OF ADVERSE EVENTS	14
8.2	EXPECTED NON-SERIOUS ADVERSE EVENTS	14
8.3	SERIOUS ADVERSE EVENTS (SAEs).....	14

8.4	EXPECTED SERIOUS ADVERSE EVENTS	15
8.5	UNEXPECTED AND FATAL SERIOUS ADVERSE EVENTS.....	15
8.6	PERIOD FOR RECORDING SERIOUS ADVERSE EVENTS.....	15
9	DATA HANDLING AND RECORD KEEPING	16
9.1	CONFIDENTIALITY	16
9.2	CASE REPORT FORMS.....	16
9.3	RECORDS RETENTION.....	16
10	STUDY MONITORING, AUDITING, AND INSPECTING	17
11	ETHICAL CONSIDERATIONS.....	17
11.1	PATIENT INFORMATION SHEETS	18
12	FUNDING.....	18
13	SPONSORSHIP	18
14	PUBLICATION PLAN.....	18
15	REFERENCES.....	19

1 Study Summary

Title	Fasting Versus Non-fasting prior to elective Cardiac catheterization
Short Title	Fasting or no fasting before cardiac catheterization
Version & Date	Version 1.7 12 October 2017
Principal Investigator	[name]
Objectives	To show that there is no increased risk of peri-procedural complications between fasting and non-fasting patients as well as improved patient satisfaction when allowed to eat up to the point of elective coronary angiography/angioplasty compared to patients kept nil by mouth. We aim to
Methodology / Design	Prospective single centre, single blinded (investigator) randomized Study Consented patients will be randomised in 1:1 ratio to either standard hospital fasting policy or allowed to eat freely up to the point of transfer to the Catheter Laboratory.

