2.2 Study Objectives

- To show that allowing patients to eat freely up to the point of elective coronary angiography/angioplasty is not associated with any increased risk of nausea, vomiting, abdominal pain, emergency intubation or aspiration pneumonia compared to patients kept nil by mouth.
- To show improved patient satisfaction when allowed to eat up to the point of elective coronary angiography/angioplasty compared to patients kept nil by mouth.

We aim to provide evidence from a prospective study to help the development of guidelines that can be implemented nationally and internationally regarding pre procedural care of cardiac patients.

3 Study Design

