3.4 Secondary Study Endpoints

- Patient satisfaction
- Incidence of hypoglycaemia (blood sugar < 3.6 mmol/l) as assessed by finger prick test
- Incidence of hypotension (SBP<90 mmHg and /or DBP<60 mmHg)
- 30 day chest infection rate

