7.2 Statistical Methods

Our composite primary endpoint will be analysed using 95% confidence interval between the fasting and non-fasting group and the event rate will be compared using the Fisher's exact test. Categorical secondary outcomes will be presented as number and percentages and compared between the two groups using the Chi-square test or Fisher's exact test. Secondary continuous outcomes will be presented as mean and standard deviation and compared using the independent samples t-test. P-values will be used to assess evidence of difference. Any P value < 0.05 will be considered significant.

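### The categorical secondary safety outcomes (30-day chest infection, hypotension) are judged by a P value with no interval, which cannot support a no-increased-risk aim; if fasting-arm rates are below about 5%, a true doubling would more often than not be non-significant

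*Combined protocol and SAP*

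**What the plan says.** Section 7.2 treats the two classes of endpoint differently. The primary composite is given a 95% confidence interval together with Fisher's exact test. For the others: "Categorical secondary outcomes will be presented as number and percentages and compared between the two groups using the Chi-square test or Fisher's exact test". The reading rule that follows is "P-values will be used to assess evidence of difference. Any P value < 0.05 will be considered significant". The statistical row of the section 1 summary repeats this plan. The opening of section 7 mentions intervals in connection with the composite and says only that the secondary endpoints will be compared.

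Section 3.4 lists the secondary endpoints. Three are binary safety outcomes: hypoglycaemia, hypotension (a systolic limb below 90 mmHg and/or a diastolic limb below 60 mmHg) and "30 day chest infection rate". Section 3.2 provides a day-30 telephone call to check for chest infection.

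The aim is worded in two ways. The section 1 summary says "To show that there is no increased risk of peri-procedural complications between fasting and non-fasting patients". The first objective in section 2.2 is narrower, namely that eating freely "is not associated with any increased risk of nausea, vomiting, abdominal pain, emergency intubation or aspiration pneumonia compared to patients kept nil by mouth". It names neither hypotension nor 30-day chest infection.

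**The concern.** The trial sets out to show an absence of added harm. For the two secondary safety outcomes discussed here, the only stated criterion is a test whose null hypothesis is that absence. Failing to reject it shows only that the data did not contradict it. With few events, that is the likely result whether or not eating before the procedure raises the rate.

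Chest infection matters most. Section 7 has the composite recorded around the procedure and again within 8 hours, so the day-30 call is the planned comparison that looks for a late respiratory consequence. The 200 per group in section 7.1 was justified on the primary event rate, with no reference to these outcomes. Without an interval, nothing in the planned output says how large an increase the data leave open.

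**Working it through.** **Inputs from the documents.** 200 per arm (section 7.1), 1:1 allocation (sections 1 and 3.2), significance at P<0.05 (section 7.2). The test is taken as two-sided, because the plan does not say.

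**Assumed inputs.** The documents give no rate for chest infection or hypotension. The only expected rate is 1-2%, for nausea and vomiting (section 11). Fasting-arm rates from 1% to 15% are therefore tried.

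**The plan's own figure.** Section 7.1 gives an upper limit of 1.5% for 0 events in 200. The rule of three gives 3/200 = 1.50%, and the exact one-sided 95% limit is 1 - 0.05^(1/200) = 1.49%. The figure reproduces as a one-sided limit; the two-sided exact limit is 1 - 0.025^(1/200) = 1.83%. No corresponding figure is stated for any secondary outcome.

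**Chance that a true doubling is non-significant.** Let X and Y be the fasting and non-fasting counts, with X ~ Bin(200, p) and Y ~ Bin(200, 2p). Sum Pr(X=x)·Pr(Y=y) over all tables with P≥0.05. The plan names two tests without saying when each applies, so two rules are shown: Fisher throughout, and uncorrected Chi-square when expected counts are at least 5, otherwise Fisher. With equal arms the expected event count per arm is half the total, so the second rule uses Chi-square from 10 events in total.

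| Fasting v non-fasting | Fisher | Chi-square where expected counts allow |
|---|---|---|
| 1% v 2% | 96% | 95% |
| 2% v 4% | 87% | 80% |
| 3% v 6% | 78% | 70% |
| 5% v 10% | 59% | 53% |
| 10% v 20% | 23% | 19% |
| 15% v 30% | 6% | 5% |

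The chance falls through 50% at a fasting rate of about 6.1% (Fisher) or 5.4% (Chi-square). Below about 5%, a doubling is therefore non-significant more often than not under either rule. At 10% and above it is usually detected.

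**What an interval would add.** Take 8/200 non-fasting v 4/200 fasting:

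- Fisher P=0.38 (Chi-square P=0.24).
- Observed difference: 4.0% - 2.0% = 2.0 points.
- Wilson 95% limits: 2.04% to 7.69% for 8/200, and 0.78% to 5.03% for 4/200.
- Newcombe lower limit: 2.0 - √[(4.0-2.04)² + (5.03-2.0)²] = 2.0 - 3.6 = -1.6 points.
- Newcombe upper limit: 2.0 + √[(7.69-4.0)² + (2.0-0.78)²] = 2.0 + 3.9 = +5.9 points.

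Other tables with an observed doubling behave the same way:

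| Events, non-fasting v fasting | Fisher P | Difference, points (Newcombe 95% interval) |
|---|---|---|
| 4 v 2 | 0.69 | +1.0 (-1.8 to +4.1) |
| 12 v 6 | 0.23 | +3.0 (-1.2 to +7.5) |
| 20 v 10 | 0.086 | +5.0 (-0.2 to +10.4) |

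All four tables are non-significant, yet each upper limit lies several points above zero.

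**The case against.** **The size depends on a rate the documents do not give.** This stands. A reader might infer that a doubled rate would usually go undetected for both outcomes. The documents do not support that without a condition. Hypotension is defined broadly and could plausibly reach 10% or more, where a doubling is missed only about one time in four or five.

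**The link to the aim is indirect.** This stands in part. Section 2.2 lists five events and neither outcome is among them. The link runs through the general wording of the section 1 summary, the day-30 call in section 3.2, and the closeness of chest infection to the aspiration pneumonia that section 2.2 does name. Hypoglycaemia is different: section 2.1 presents it as a risk of fasting, so a test of difference suits it.

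**Late harm is captured elsewhere.** Intubation and aspiration are in the composite, which has an interval, and serious adverse events are recorded for one month (section 8.6). So the safety aim does not rest wholly on the secondary outcomes. Adverse event recording is not a planned between-arm comparison, however.

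**The plan never says that P≥0.05 will be read as no increase.** Correct. Its words are "P-values will be used to assess evidence of difference". A reader might infer that a non-significant result will be reported in support of ending fasting, but that would be a prediction about reporting. What can be said is that no rule is given against that reading, although the aim invites it.

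**Counts by arm are planned, so anyone could compute the interval, and the study calls itself a pilot.** Both are true and limit the harm. Neither makes the stated criterion suited to the aim, and section 2.2 also looks ahead to national and international guidelines.

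**Examples can be chosen to flatter the point.** A table of 7 v 1 gives Fisher P=0.068 against a Newcombe interval that excludes zero. That mostly reflects disagreement between methods, since Chi-square gives P=0.032. It is not relied on here; 8 v 4 is non-significant by both tests.

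**Conclusion.** The point holds in a conditional form. The plan gives 30-day chest infection and hypotension no effect estimate and no interval, and its only criterion is a P value against no difference. That cannot support an aim of no increased risk at any event rate, because even a well-powered test does not state how much harm remains possible.

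The practical size depends on an assumption. With 200 per arm and a fasting rate below about 5%, which is plausible for chest infection but not documented, a true doubling would be non-significant more often than not. The chance ranges from about 95% at 1% v 2% to between 53% and 59% at 5% v 10%. At 10% v 20% it is 19-23%. The calculation also assumes two-sided tests and complete data.

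This is a worthwhile reporting correction for secondary outcomes. It is separate from the primary endpoint, for which an interval is already planned.

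**What to change.** Keep the existing sentence on categorical secondary outcomes, so that the planned counts, percentages and tests remain for every such item. Add the following to section 7.2 and to the statistical row of the section 1 summary:

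> For 30-day chest infection and hypotension, the non-fasting minus fasting risk difference will also be reported with a two-sided 95% confidence interval (Newcombe or Miettinen-Nurminen). A P value of 0.05 or more will not be taken as evidence of no increased risk; conclusions will state the largest increase the interval does not exclude.

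The same interval may be reported for hypoglycaemia, without the no-increase wording.

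The cost is two sentences in two places, with no new patients, visits or data. The downside is a less favourable safety statement, because at this sample size the upper limits will be several points wide.

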7.3 Interim Analyses

Final Analysis will take place once all data is collected. However, if sequentially the first 10 patients in the non-fasting group show signs of an event rate in excess of that shown in the fasting group as demonstrated by non-overlapping confidence intervals then stopping rules will be applied. For this pilot study, this will be monitored by the Chief Investigator.

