4.3 Randomisation Process

Randomisation will take place in pre-procedure assessment clinic in a 1:1 ratio using sealed enveloped method. This information (whether fasting or not) will be relayed to the patient at the time of pre-procedure assessment and also stored on a spreadsheet with study number the only identifying factor. This will be password protected with individuals directly involved having access to this. This data will also be backed up on a password protected computer in the catheter laboratory.

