7.1 Sample Size Determination

With 200 participants in each group, if none of the participants has an event then the upper limit of the 95% confidence interval for event rate would be 1.5%. Hence if both groups, fasting and non-fasting, have no events recorded then it is highly unlikely that the event rate in the two groups would differ by more than 1.5%. Provided that a difference of 1.5% in event rate is deemed not clinically meaningfully different; then 200 participants in each group would demonstrate that not fasting has a similar event rate to fasting.

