7.4 Subject Population(s) for Analysis

All participants will be used in analysis. Intention to treat analysis will be used to avoid the effects of crossover and dropout providing unbiased comparisons among the treatment groups.

8 Safety and Adverse Events

Any complications will be treated in the usual way irrespective of study arm included in.

The Chief Investigator will be continuously monitoring the data and if sequentially the first 4 (15%) patients in the non-fasting group show signs of an event rate in excess of that shown in the fasting group, as demonstrated by non-overlapping confidence intervals then stopping rules will be applied.

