9.3 Records Retention

All records will be archived for 5 years in line with the Trust R&D Policy.

10 Study Monitoring, Auditing, and Inspecting

The investigator will permit study-related monitoring, audits and inspections by the Ethics Committee, the Sponsor and the Research Governance Manager.

Participation as an investigator in this study implies adherence to the principles and responsibilities of the Research Governance Framework, ICH/GCP and Directive 2000/20/EC

11 Ethical Considerations

The patient will receive a detailed description of the study in the patient information sheet send together with pre-procedure assessment letter by mail (around 1 week before the pre-procedure assessment clinic date) to give him/her time to think about the study. Then, at the pre-procedure assessment clinic, they will have the opportunity to ask questions with one of the research team and to answer any queries. Any patient will have the right to abstain from taking part into the study or to withdraw after taking part without affecting the standard of care they are receiving.

The Chief Investigator will ensure that the risk of the study does not outweigh the benefit at any point during the study time, and if so, the study will be prematurely terminated.

The benefit /risk of taking part into the study will be adequately explained to the patients. There will be no direct benefit to the patient from taking part in this study. However, the information gained from the study will help improve the quality of service offered to the patients, increase their satisfaction, may aid in changing the current practice and avoiding unnecessary delay to the patients. The potential risk will be made clear which is the occurrence of nausea and vomiting at an expected rate of 1-2% and no expected emergency endotracheal intubation or aspiration pneumonia cases.

Once patient is enrolled in the study, all his personal information will be anonymized with the only identifier the study number. All patient data will be password protected on the computer in the cath lab. All health professionals involved in the study and patient care will have access to this

information if required. Only the CI will have access to identify the patient personal data for the purpose of safety.

To ensure un-biased result, an adequate randomization process with intention to treat analysis will be undertaken. Analysis will be done by the Sub-Investigator who is blinded to group allocation.

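### As worded, the only between-arm stopping comparison covers the first 10 (or first 4) of 200 non-fasting patients; no boundary or scheduled look is stated for the rest

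*Combined protocol and SAP*

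**What the plan says.** Section 7.1 sizes the trial at 200 per arm ("With 200 participants in each group"), and section 4.3 randomises "in a 1:1 ratio using sealed enveloped method".

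Section 7.3 places the main analysis after all data are in and adds one exception: "if sequentially the first 10 patients in the non-fasting group show signs of an event rate in excess" of the fasting group's, "as demonstrated by non-overlapping confidence intervals then stopping rules will be applied". Section 8 gives the same rule with a different span: "The Chief Investigator will be continuously monitoring the data and if sequentially the first 4 (15%) patients in the non-fasting group". Neither section states the confidence level, the interval method, how many fasting patients form the comparison, or what the stopping rules are once invoked.

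Other safeguards run throughout and carry no number:

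- Section 8: the Chief Investigator monitors the data continuously.
- Section 3.5: the study may end early over a safety issue.
- Sections 8.3 and 8.5: serious adverse events go to the Chief Investigator within 7 days. Emergency intubation, aspiration and death also go to the sponsor.
- Section 11: "The Chief Investigator will ensure that the risk of the study does not outweigh the benefit at any point during the study time", with early termination otherwise.

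Section 8.2 classes nausea, vomiting and abdominal pain as expected and non-serious, and does not require them to be reported to the sponsor.

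**The concern.** The authors saw a need for an objective comparison between arms during recruitment and wrote one. As worded, it applies only at the very start, when two separate intervals can hardly part. An excess of gastrointestinal events that becomes plain at 50 or 100 patients per arm meets no stated criterion. Whether to continue then rests on one person's judgement, with no threshold or schedule to refer to. The serious components have their own route to the sponsor; the common components do not. Settling whether the rule says 4 or 10 would not change this, since either leaves at least 190 patients outside it.

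**Working it through.** **Inputs from the documents.** 200 per arm (7.1); 1:1 allocation (4.3); span of 10 (7.3) or 4 (section 8); trigger of non-overlapping intervals (both); expected nausea and vomiting rate of 1-2% (section 11).

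**Assumptions, because the plan is silent.** 95% two-sided intervals, Clopper-Pearson (exact) or Wilson; equal arm sizes unless stated; a fasting event rate of 1.5%, the middle of 1-2%.

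**The plan's own figures.** The 1.5% upper limit for 0 of 200 in 7.1 reproduces as 3/200 = 1.50%, or as a one-sided exact limit, 1 − 0.05^(1/200) = 1.49%. A two-sided exact limit is 1.83%. This figure does not drive the point. The 15% attached to 4 patients in section 8 does not fit 200 per arm: 4/200 = 2%, and 15% of 200 is 30. It is close to 4/25 = 16%, where 25 is half of the 50 pilot patients named in section 12.

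**Span.** 10/200 = 5%, leaving 190 patients; 4/200 = 2%, leaving 196.

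**What the rule needs inside its span.** It fires when the lower limit for non-fasting exceeds the upper limit for fasting.

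- 10 v 10, exact: the upper limit for 0/10 is 30.8%. The lower limit is 26.2% for 6/10 and 34.8% for 7/10, so 7 v 0 is needed (9 v 1 if one fasting patient has an event).
- 10 v 10, Wilson: the upper limit for 0/10 is 27.8%. The lower limit is 23.7% for 5/10 and 31.3% for 6/10, so 6 v 0 is needed (8 v 1).
- 10 against 0/25, exact: the upper limit is 13.7%. The lower limit is 12.2% for 4/10 and 18.7% for 5/10, so 5 are needed.
- 4 v 4, exact: the lower limit for 4/4 is 39.8% and the upper limit for 0/4 is 60.2%, so it cannot fire. Wilson needs 4 v 0.

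**Chance of firing at 10 v 10, true rates 20% v 1.5%.** P(no fasting event) = 0.985^10 = 0.860. P(one) = 10 × 0.015 × 0.985^9 = 0.131.

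- Exact: P(X ≥ 7) = 0.000864, and 0.000864 × 0.860 = 0.00074, or 0.07%. The 9 v 1 term is negligible.
- Wilson: P(X ≥ 6) = 0.00637, and 0.00637 × 0.860 + 0.000078 × 0.131 = 0.0055, or 0.55%.
- With a fasting rate of 1% the results are 0.08% and 0.6%. With a non-fasting rate of 50% v 1.5% they are 15% and 33%.
- Against 25 fasting patients (exact): 0.0328 × 0.985^25 + 0.00637 × 25 × 0.015 × 0.985^24 = 0.0225 + 0.0017 = 0.024, or 2.4%.

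**The same criterion carried forward, for illustration.** Exact 95% intervals on cumulative counts at 10, 25, 50 and then every 25 per arm to 200. Probability of having fired:

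| True rates (non-fasting v fasting) | by 50 per arm | by 100 | by 200 |
|---|---|---|---|
| 20% v 1.5% | 56% | 97% | >99% |
| 10% v 1.5% | 6% | 36% | 84% |
| 5% v 1.5% | 0.2% | 2% | 17% |

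**False stops over all looks, same rate in both arms.**

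| Common rate | Exact | Wilson |
|---|---|---|
| 1.5% | 0.03% | 0.1% |
| 5% | 0.4% | 0.6% |
| 10% | 0.6% | 1.0% |
| 20% | 0.7% | 1.3% |

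**The case against.** A reader might infer that nothing protects patients after the tenth. The documents do not support that. Monitoring by the Chief Investigator, termination for safety, serious event reporting and the risk-benefit duty all continue, and intubation, aspiration and death reach the sponsor. This objection stands, and it narrows the gap to a numerical criterion, chiefly for events that the plan itself calls non-serious.

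A reader might also infer that the plan ends the rule at patient 4 or 10. It never says so; the limit comes from the wording and from silence about later patients. Next to continuous monitoring, "if sequentially the first 4 (15%) patients in the non-fasting group show signs of an event rate in excess" could have been meant as a running count of patients with events, 4 being 16% of 25. The text does not say this either. On that reading 4/25 v 0/25 still gives overlapping exact intervals (4.5-36.1% v 0-13.7%). If a running rule was intended, writing it down is the remedy.

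The documents also call the study a pilot, and against 25 per arm the first 4 to 10 are 16-40%. But sections 1, 3.5 and 7.1 all support 400 patients.

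Finally, 7 v 0 is not the plan's own threshold. It depends on the assumed method, level and fasting denominator, and a larger fasting group lowers the bar inside the span. It does nothing for later patients.

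**Conclusion.** The point holds in a limited form. As worded, the only between-arm stopping comparison reaches 2-5% of the non-fasting arm, and no boundary or scheduled look is stated for the other 190 to 196 patients. Within its span it would rarely fire: 0.07% (exact) or 0.55% (Wilson) at a true 20% v 1.5% with 10 per arm, and 2.4% (exact) against 25 fasting patients. These figures rest on 95% intervals and a 1.5% fasting rate, neither fixed by the plan for this purpose; the span itself rests on the wording alone.

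It would be wrong to conclude that extending the criterion makes monitoring sensitive. It catches a large excess early, but 5% v 1.5% is flagged in only about 17% of trials by 200 per arm. That is a difference of 3.5 points, more than twice the 1.5 points used in 7.1. This is a cheap improvement that should be made, not a defect that leaves the trial without safety oversight.

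**What to change.** Reconcile sections 7.3 and 8 into one rule, including the 4, the 10 and the 15%. State the interval method, the confidence level and the fasting comparison group. State that the criterion applies to cumulative events in both arms at looks scheduled across all 200 per arm, in addition to the discretionary safeguards. The number of looks and the threshold are for the sponsor to set; the 25-patient spacing above is only an illustration. The sponsor should choose the threshold knowing that non-overlap of two 95% intervals usually misses a moderate excess.

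The cost is wording in two sections and a running two-arm count by the person already monitoring, with no extra patients or staff. There are two downsides. False stops are about 0.03-0.7% (exact) or 0.1-1.3% (Wilson) for common rates of 1.5-20%. The Chief Investigator would also see repeated by-arm counts in a trial that section 1 describes as investigator-blinded, although section 8 already has that person comparing the arms.
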